## **Background and Significance**

Sleep-Related Eating Disorder (SRED) is a parasomnia characterized by arousals from sleep, compulsive consumption of food, poor sleep quality, and morning anorexia. SRED is generally more prevalent in females, with onset in early adulthood. SRED is thought to be closely related to Night Eating Syndrome (NES), another night-time eating disorder. It is thought that SRED and NES are related processes in which night-time eating occurs along a variable spectrum of arousal; individuals with NES are fully conscious during their night-eating episodes, whereas individuals with SRED are only partially conscious during their night-eating episodes. This nosology is reflected in the most recent diagnostic criteria for SRED in the International Classification of Sleep Disorders, Second Edition (ICSD-2) in which the level of consciousness is not a diagnostic criteria, stressing rather, that the sleep-related eating behavior is involuntary in nature.

Night Eating Syndrome was first reported in 1955, however the syndrome was not further investigated and defined until almost 30 years later, and still lacks standard diagnostic criteria. Its prevalence in the general population is uncommon, estimated at 1.5%, but more common in the severely obese population, with estimates ranging from 9 to 43%. Onset of the syndrome has been linked to stressful life experiences. Individuals with NES experience morning anorexia, consume over half of their daily caloric intake after 6 PM and suffer from insomnia. NES patients have full awareness of their night-eating episodes; however, the binge eating is compulsive and difficult to suppress.

Sleep-Related Eating Disorder has only been reported in the last decade. It has been estimated that approximately 1% of young adults have exhibited this behavior, which usually occurs nightly, sometimes several times a night. Patients with SRED may have variable level of awareness during an episode of night eating, often describing their eating occurring while they are "half awake" or "half asleep". Amnesia may be present the morning after an episode, and thus the occurrence of such an episode must be inferred from evidence observed in the morning. Individuals tend to eat high calorie foods, and some consume inappropriate foods (e.g. frozen foods, non-nutritive substances) during episodes. Weight gain is often associated with this behavior. Sleep disorders such as Restless Legs Syndrome and somnambulism are common among these patients.

Current treatments for SRED have been directed towards treating any underlying sleep disorder, eating or psychiatric disorder. Selective serotonin reuptake inhibitors (SSRIs), dopaminergic agonists, benzodiazepines, anorectics, hypnotics and opioids have been used, but success in treatment has varied.

## **Preliminary Reports with Topiramate**

Preliminary reports of topiramate in individuals with NES or SRED indicate that topiramate may be a beneficial in the treatment of these syndromes. In an open-label study of four subjects (two with NES, two with SRED), one subject had complete elimination of night eating (NES subject), two had a 75- $<$ 100% reduction in night eating, and one had a 50- $<$ 75% reduction in night eating. The dose of topiramate ranged from 100 mg-400 mg daily, with an average dose of 216 mg. Subjects also experienced weight loss ranging from 15-33 pounds. Topiramate was well tolerated. In addition to this study, a case study of a patient with NES and co-morbid Post-traumatic Stress Disorder reported improvement of NES with topiramate treatment. More recently, there have been two larger case series published examining the use of topiramate in SRED. In the case series of 17 patients conducted by Schenck and Mahowald, topiramate fully/substantially controlled in all 11 subjects who were able to continue with topiramate therapy [6 subjects discontinued the medication; 4 due to lack of efficacy and 2 due to side effects (urticaria, weight gain)]. In the retrospective case series conducted by Winkelman, over two-thirds (17/35) patients treated with topiramate were considered responders. These reports suggest that further investigation of topiramate as a potential treatment for SRED is warranted.

## **Topiramate Background**

Topiramate is a sulfamate-substituted monosaccharide derived from fructose. It is structurally distinct from any other anti-epileptic medication. Topiramate is a structurally novel compound that is an effective anticonvulsant with a good safety profile after oral administration in animals and humans. Topiramate has been approved for marketing in the United States and most European Union countries for adjunctive treatment of pediatric and adult patients with partial onset seizures, Lennox-Gastaut syndrome, or primary generalized tonic-clonic seizures. It has also been approved as monotherapy in some countries. Topiramate is currently under investigation for a number of other disorders including migraine, bipolar disorder, and essential tremor. For a complete profile, see the package insert.

## **Nonclinical Studies**

### Pharmacologic Profile

Topiramate has multiple mechanisms of action that may contribute to its anti-convulsant properties, as well as its potential therapeutic effect in other Central Nervous System (CNS) disorders. First, the drug inhibits voltage gated sodium channels and thus suppresses action potentials associated with sustained repetitive cell firing. Second, topiramate augments the inhibitory chloride ion influx mediated by  $\gamma$ -aminobutyrate (GABA). This is not blocked by flumazenil suggesting that the mechanism is different from that of benzodiazepines. Third, topiramate antagonizes the ( $\alpha$ -amino-3-hydroxy-5-methylisoxazole-4-propionic acid) AMPA/kainate subtype of the glutamate receptor. It has no effect on the N-methyl-D-aspartate (NMDA) subtype. Fourth, topiramate reduces the firing of high voltage-activated (L-type) calcium channels. It is also a weak inhibitor of some isoenzymes of carbonic anhydrase.

### Toxicology

The data for preclinical toxicology studies were obtained for dosage levels up to the maximum tolerated doses. Female rats and male and female dogs have received higher systemic exposure to topiramate than the highest anticipated clinical exposure in humans. It is notable that the female rat appears to provide the best animal model for human metabolism of topiramate.

In general, acute and long-term oral exposure of mice, rats, dogs, and rabbits to topiramate was well tolerated. Hyperplasia of the gastric and urothelial cells seen in shorter term studies did not progress to neoplasia after lifetime exposure in rats or mice and has not been reported during clinical studies. Smooth muscle tumors of the urinary bladder in mice appear to be unique to the species. There is no known clinical counterpart; therefore, these tumors were not considered to be of relevance to man. As with many other anticonvulsants, topiramate is teratogenic in mice, rats and rabbits. The teratologic effects of topiramate seen in rats and rabbits appear to be related to carbonic anhydrase inhibition. Reductions in weight of progeny were also indicated by reproductive studies in these species, but no effects on fertility were observed for male or female rats. Based on results of in vitro and in vivo mutagenicity assays, topiramate does not show genotoxic potential. For further background on the toxicology of topiramate, see the Investigator's Brochure.

### Pharmacokinetic Profile

Studies in humans show that topiramate is rapidly absorbed, with peak concentrations occurring at approximately 2 hours following an oral dose. The bioavailability of topiramate from tablet formulation is approximately 80% compared to a solution. Bioavailability is not affected by food. Topiramate exhibits linear pharmacokinetics with dose proportional increases in plasma concentration over the 100-400 mg b.i.d. (200-800 mg/day) dose range studied. Topiramate is poorly bound to plasma proteins, 13-17% (over the concentration range of 1-250 mcg/ml), but there is a low-capacity erythrocyte binding site for the drug. The mean plasma elimination half-life is 21 hours after single or multiple doses. Steady state is reached in approximately 4 days in subjects with normal renal functioning. The major route of elimination is via the kidneys.

Topiramate is not extensively metabolized and is primarily eliminated unchanged in the urine (approximately 70% of an administered dose). Six metabolites have been identified, none of which constitutes more than 5% of an administered dose. The metabolites are formed via hydroxylation, hydrolysis, and glucuronidation. Overall, plasma clearance is approximately 20 to 30 mL/min in humans following oral administration. Evidence of renal tubular reabsorption of topiramate was demonstrated in rats given probenecid to inhibit tubular reabsorption along with topiramate, where a significant increase in renal clearance of topiramate was observed.

### **OBJECTIVE**

The primary objective of this study is to investigate the efficacy and safety of topiramate compared to placebo in the treatment of Sleep-Related Eating Disorder.

### **OVERVIEW OF STUDY DESIGN**

This is a single center, 13-week, outpatient, randomized, double-blind, placebo-controlled, parallel group, pilot study of topiramate in subjects with Sleep-Related Eating Disorder.

After giving informed consent, subjects who meet all the inclusion and exclusion criteria may be enrolled. The study will consist of two phases:

- pre-randomization phase (up to 56 days prior to randomization), consisting of a screening/washout period (up to 42 days) and a prospective baseline period (14 days);
- treatment phase, consisting of titration period: up to 9 weeks; maintenance period: 4 weeks; taper period: 2 weeks.

The study medication will be titrated to 300 mg/day or the subject's minimum effective dose. Subjects must reach a minimum dose of 25 mg/day after the second week of titration. The taper period will last approximately two weeks during which subjects will gradually reduce their medication until they are no longer taking the study medication.

## **SUBJECT POPULATION**

### **General Considerations**

This study will enroll up to 240 subjects with the goal of randomizing 40 subjects with Sleep-Related Eating Disorder. The specific inclusion and exclusion criteria for enrolling subjects in this protocol are outlined below. Our estimated completion date for the study is January 2015.

### **Inclusion Criteria**

Subjects must satisfy the following criteria before entering the study:

1. Subjects must have a diagnosis of the following for at least 6 months:  
  
Sleep-Related Eating Disorder, defined as (according to ISCD-2 criteria):
  - A. Recurrent episodes of involuntary eating and drinking occur during the main sleep period.
  - B. One or more of the following must be present with the recurrent episodes of involuntary eating and drinking:
    - i. Consumption of peculiar forms or combinations of food or inedible or toxic substances
    - ii. Insomnia related to sleep disruption from repeated episodes of eating, with a complaint of nonrestorative sleep, daytime fatigue, or somnolence
    - iii. Sleep related injury
    - iv. Dangerous behaviors performed while in pursuit of food or while cooking food
    - v. Morning anorexia
    - vi. Adverse health consequences from recurrent binge eating of high-caloric foods
  - C. The disturbance is not better explained by another sleep disorder, medical or neurologic disorder, mental disorder, medication use, or substance use disorder
2. Subjects must experience 3 nights per week of nocturnal eating during the 14-day prospective baseline period prior to Visit 2.
3. Subjects must be between 18 and 75 years of age.
4. Subjects must be able to take oral medication in capsule form, adhere to medication regimens and be willing to return for regular visits.
5. Subjects must have observed the designated washout periods for prohibited medications outlined under the Concomitant Therapy section of this protocol.
6. Female subjects must be:
  - postmenopausal for at least one year, surgically sterile, or
  - practicing an effective method of birth control (e.g., contraceptive injections, intrauterine device, double-barrier method, contraceptive patch, male partner sterilization, abstinence)

and agree to continue abstinence or to use an acceptable method of contraception, as listed above, should sexual activity commence) before entry and throughout the study

- If taking prescription oral contraceptives, must agree to also use a barrier method of birth control throughout the study since topiramate may affect the metabolism of prescription oral contraceptives.
  - Have a negative urine pregnancy test at Visit 2 (Day 1).
7. Subjects must be able to read and comprehend written instructions, and be willing and able to comply with protocol requirements.
  8. Subjects must have signed an informed consent document indicating that they understand the purpose of and procedures required for the study and are willing to participate in the study

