### **Exclusion Criteria**

Subjects will be excluded from the study if they meet any of the following criteria:

1. Subjects with evidence of untreated primary sleep disorders (e.g., Obstructive Sleep Apnea, Restless Legs Syndrome, Periodic Leg Movements of Sleep) as determined in the sleep screening questionnaire and clinical history.
2. Subjects who have a DSM-IV diagnosis of substance dependence or abuse (with the exception of nicotine) that has been active within the past 6 months.
3. Subjects taking exclusionary medications, such as benzodiazepines/benzodiazepine receptor agonists, tricyclic antidepressant medications or antipsychotics as these medications have been reported to cause SRED, who are unable or unwilling to complete the required washout of these medications.
4. Subjects with an active or unstable major psychiatric disorder requiring further treatment (e.g., major depressive disorder). Subjects with clinically significant depression defined by a HAM-D >20 or who, in the investigator's judgment might require intervention with either pharmacological or non-pharmacological therapy over the course of the study, will also be excluded.
5. Subjects with an active daytime DSM-IV-TR™ diagnosis of Anorexia Nervosa or Bulimia Nervosa within the 3 months prior to screening.
6. Subjects judged clinically to be at serious suicidal or homicidal risk.
7. Subjects with a body mass index (BMI)  $\geq 50$  kg/m^2.
8. Subjects who have positive urine drug screening (phencyclidine, cocaine, amphetamines, tetrahydrocannabinol, and opiates) at Visit 1 (Day -14).
9. Subjects who report consumption of more than 2 alcoholic beverages daily, 14 or more alcoholic beverages weekly
10. Subjects who report consumption of more than 4 beverages containing caffeine daily.

11. Subjects who are rotating or third shift workers.
12. Subjects who are pregnant or lactating.
13. Subjects with a history of recurrent nephrolithiasis or on another carbonic anhydrase inhibitor.
14. Subjects with progressive or degenerative neurological disorders or a structural disorder of the brain from birth, trauma or past infection.
15. Subjects who have recently had or are planning to have surgery.
16. Subjects who have previously been treated with topiramate and discontinued treatment due to an adverse event or subjects with a known hypersensitivity to topiramate.
17. Subjects who have previously taken Topiramate.
  

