#### Visit 1\* (Day -14)

1. Review inclusion/exclusion criteria
2. Assess concomitant medications
3. Obtain weight
4. Obtain non-fasting clinical laboratory tests as follows:
  - Urine Drug Screen [cocaine, amphetamines, methamphetamines, benzodiazepines, tetrahydrocannabinol (THC), and opiates].
  - Hemoglobin A1C
  - Creatinine (creatinine clearance will be calculated using standard formula)
5. Perform urine pregnancy test (subjects of childbearing potential only)
6. Administer the Three Factor Eating Questionnaire (TFEQ)
7. Administer the Sheehan Disability Scale
8. Dispense sleep and night eating diary
9. Record adverse events
10. Schedule return visit

\*Visits 1A and 1 may be combined for subjects who do not require washout from prohibited medications.

Subjects who are eligible for study entry based on the results of the above will be instructed to return for Visit 2 (Day 1).

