#### **Double-Blind Phase**

Subjects who continue to meet all entrance criteria will be randomized for study entry at Visit 2 (Day 1). The following procedures will be performed:

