#### Visit 2 (Day 1)

1. Review inclusion/exclusion criteria
2. Assess concomitant medications
3. Administer the Medical Outcome Study (MOS) Sleep Scale
4. Administer the Epworth Sleepiness Scale
5. Collect and review sleep and night eating diary
6. Dispense sleep and night eating diary
7. Record adverse events
8. Dispense study medication
9. Schedule return visit in one week

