### TIME AND EVENTS SCHEDULE

	Visit 1A (Day -56)	Visit 1 (Day -14)	Visit 2 (Day 1)	Visit 3 (Day 7)	Phone Contact (Day 14)	Visit 4 (Day 21)	Phone Contact (Day 28)	Visit 5 (Day 35)	Phone Contact (Day 42)	Visit 6 (Day 49)	Phone Contact (Day 56)	Visit 7 (Day 63)	Phone Contact (Day 77)	Visit 8 (Day 91)	Visit 9 (Day 105)
Informed Consent	X														
Review Inclusion/Exclusion Criteria	X	X	X												
Concomitant Medication Review	X	X	X	X	X	X	X	X	X	X	X	X	x	X	X
Medical & Psychiatric History	X														
Physical Examination	X														
Neurologic Examination	X														
SCID Eating Disorders	X														
Weight	X	X	X	X		X		X		X		X		X	X
Urine Pregnancy Test		X						X				X			
Urine Drug Screen		X													
Blood HbA1C		X*												X	
MOS			X					X				X		X	
Epworth Sleepiness Scale			X					X				X		X	
HAM-D	X							X				X		X	
TFEQ		X												X	
EAT	X														
Sheehan Disability Scale		X												x	
Dispense Sleep and Night- Eating Diary		X	X	X		X		X		X		X			
Review Sleep and Night- Eating Diary			X	X	X	X	X	X	x	X	x	X	X	X	
Record Adverse Events		X	X	X	X	X	X	X	X	X	X	X	X	X	X
Dispense Study Medication			X	X	X	X	X	X	x	X	x	X	x	X	
Collect study medication and perform drug accountability				x		x		X		X		X		x	X

\*Creatinine also tested at visit 1

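### Inclusion 6 requires a negative pregnancy test on Day 1, but neither the Visit 2 procedure list nor the Visit 2 column of the schedule provides for it

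*Combined protocol and SAP*

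**What the plan says.** Inclusion Criteria, item 6, sets a condition for female subjects: "Have a negative urine pregnancy test at Visit 2 (Day 1". The Double-Blind Phase section makes eligibility a condition of randomisation on that day: "Subjects who continue to meet all entrance criteria will be randomized for study entry at Visit 2 (Day 1".

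The Visit 2 (Day 1) list has nine items. The first is "Review inclusion/exclusion criteria" and the eighth is "Dispense study medication". The others cover concomitant medication, the MOS and Epworth scales, collecting and dispensing the diary, adverse events and scheduling. None is a pregnancy test.

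The visit lists place the test at Visit 1 (Day -14, item 5), Visit 5 (Day 35, item 3) and Visit 7 (Day 63, item 3). The Visit 1 line reads "Perform urine pregnancy test (subjects of childbearing potential only". In the Time and Events Schedule, the row "Urine Pregnancy Test" is marked at the same three visits and is blank at Visit 2.

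**The concern.** One part of the protocol makes a Day 1 result a condition of entry, and the two parts that staff work from on the day do not call for it. The Toxicology section describes topiramate as teratogenic in three animal species, exclusion 12 bars pregnant subjects, and the Pregnancies section requires prompt withdrawal. The Day 1 test is the only pregnancy check placed immediately before the first dose.

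If it is missed, two things follow. An affected subject is randomised without a required eligibility result, which is a protocol deviation. And a pregnancy that the Visit 1 test was too early to detect could be exposed to study drug until a later test or a self-report brings it to light.

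**Working it through.** The plan states no figure to reproduce here. The check is a comparison of texts followed by day counts.

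**Step 1: where the test appears.**

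| Source | Visit 1 (Day -14) | Visit 2 (Day 1) | Visit 5 (Day 35) | Visit 7 (Day 63) |
|---|---|---|---|---|
| Inclusion 6 | not named | required | not named | not named |
| Visit procedure lists | item 5 | absent | item 3 | item 3 |
| Time and Events row | X | blank | X | X |

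The row has 16 cells against 16 header cells, so the marks line up with their columns. The lists and the table also agree with each other. The blank at Visit 2 is therefore not a fault of text extraction; the mismatch is with inclusion 6.

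**Step 2: does the criteria review schedule the test?** At Visit 1 the criteria review is item 1, and the drug screen and pregnancy test are listed separately as items 4 and 5. The review is thus not the protocol's way of ordering a test at that visit. The other criterion tied to a test at a named visit is exclusion 8 ("Subjects who have positive urine drug screening", at Visit 1). It has its own line ("Urine Drug Screen") and its own table mark at that visit. The Day 1 pregnancy test has neither.

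**Step 3: time without a scheduled test.** Counting with no Day 0 (add one day to the first figure and to the total if a Day 0 is counted):

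- Last scheduled test to first dose: Day -14 to Day 1 = 14 days. It cannot be much shorter, because inclusion 2 needs a 14-day diary baseline before Visit 2.
- First dose to next scheduled test: 35 - 1 = 34 days. With the +/- 3 day visit window: 32 - 1 = 31 to 38 - 1 = 37 days.
- Total between scheduled tests: 14 + 34 = 48 days, about seven weeks.

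**Step 4: exposure that a Day 1 test would prevent.** This concerns a pregnancy detectable on Day 1 but not at Visit 1. Exposure before the next scheduled test is about 34 days (31 to 37). The Early Withdrawal section asks subjects who stop early to taper, and Study Treatments puts the taper at about 14 days. If a full taper were applied, the total would be about 34 + 14 = 48 days (45 to 51).

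**Step 5: dose over that time.** The suggested titration starts at 25 mg/day (Days 1-7) and reaches 125 mg/day on Days 29-35. If Visit 5 fell on Days 36-38 and the schedule were kept, the dose would be 150 mg/day. The rate is adjustable at the investigator's discretion, and subjects with reduced creatinine clearance titrate more slowly, so these doses are illustrative.

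**Step 6: who is affected.** Allocation is 1:1 with a goal of 40 randomised, so about 40 / 2 = 20 subjects receive topiramate. Only those of childbearing potential count. The documents do not give their share, so no expected number of exposed pregnancies can be calculated.

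**The case against.** The strongest reply is that this is an omission, with no conflict of instructions. Nothing waives the test: inclusion 6 names the test, the result and the day, and the Visit 2 criteria review cannot properly be completed for these subjects without it. That stands. A reader might infer that the protocol permits dosing without a Day 1 test, or that the schedule has no pregnancy testing at all. Neither is supported: dispensing without the result would breach inclusion 6, and the table has a pregnancy-test row with three marks.

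A second reply is that the visit lists are visibly incomplete. Weight at Visit 2 and the HAM-D at Visit 7 are marked in the table but missing from the lists, the sleep screening questionnaire in exclusion 1 has no list entry or table row, and randomisation itself is not among the Visit 2 items. This weakens any inference that an unlisted test would not be done. It does not close the gap: weight and the HAM-D can be recovered from the table, but the Day 1 pregnancy test is in neither place.

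Third, other safeguards exist: the Visit 1 test, contraception requirements (with an added barrier method for users of oral contraceptives), adverse-event contacts on Days 7, 14, 21 and 28, and withdrawal on pregnancy. They lower the risk and limit the severity of the point. None replaces a test before the first dose.

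**Conclusion.** The mismatch is real and should be corrected. If staff follow the list and table, study drug is dispensed about 14 days after the last scheduled test. A pregnancy that became detectable in that gap could then be exposed for roughly five weeks before the next scheduled test, plus any taper.

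This assumes that the subject is of childbearing potential and allocated to topiramate, that the Day 1 test is in fact missed, and that the pregnancy is not reported earlier. The dose figure further assumes that the suggested titration is followed.

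Three stronger readings should be resisted. Neither 34 days nor 125 mg/day is a ceiling, given the visit window, the taper and the adjustable titration. Pregnancies that begin after Day 1 are not part of this point, because the interval from Day 1 to Day 35 has no scheduled test whether or not the omission is repaired. And nothing here affects the primary ANCOVA of eating nights per week or the sample size, which was not set on statistical grounds.

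**What to change.** Add a urine pregnancy test for subjects of childbearing potential to the Visit 2 list, worded as in Visit 1 item 5. Place it early enough that the result is known before randomisation and dispensing. Put an X in the Visit 2 column of the Time and Events row. Keep the Visit 1 test.

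Do not reconcile the text by moving the criterion to Visit 1: that would make the document consistent but leave the 14-day gap before the first dose.

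The cost is one list line, one table mark and one urine test per subject of childbearing potential, which inclusion 6 already requires.
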